10.2.2 Secondary Endpoints

- TWPI due to AS at Months 3, 6, 12, and 18
- TWPI due to PsA at Months 3, 6, 12, and 18
- TWPI due to AS or PsA at Months 3, 6, and 12
- Evolution over time of :
 - Number of patients that are employed at each assessed visit
 - Percentage of missed working hours (absenteeism) due to AS/PsA, as measured by TWPI AS/PsA 7 days prior to each visit

- Assessment of the effect of AS/PsA on the ability to do regular daily activities during the 7 days prior to each visit (activity impairment)
- Assessment of the effect of AS/PsA on productivity while working during the 7 days prior to each visit (presenteeism).
- Health Related Quality of Life (patient reported outcome) recorded at each visit
 - HAQ-S (AS)
 - HAQ-DI (PsA)
 - DLQI (PsA)
- Disease activity measures and clinical evaluations recorded at each visit:
 - BASDAI (AS)
 - DAS28 (PsA)
 - BSA (PsA)
 - Acute phase reactants (CRP / ESR)
 - Physician assessment of disease activity (VAS)
 - Patient assessment of disease activity (VAS)
 - Patient assessment of pain (VAS).

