10.3.2 Statistical Analysis

The study is essentially descriptive. The numerical variables will be analyzed applying descriptive statistics (mean, 95% confidence interval on the mean, standard deviation, minimum, 1st quartile, median, 3rd quartile, maximum, number of observations).

Quantitative variables will be described by means of frequencies and percentages for the

different categories. For the variables recorded for both AS and PsA patients the descriptions will be given for all patients as well as separately for each subgroup.

The analysis of the evolution of the work productivity data, the health-related quality of life scores, and the disease activity measures and clinical evaluations will be based upon data collected during time windows around the foreseen routine study visits.

The relationship between disease activity and work status and between clinical evaluations and work status will be evaluated by comparing the onset data for patients currently employed and patients not employed at the baseline visit, and by comparing the data from the 18 month time window for patients currently employed and patients not employed at the corresponding visit.

The relationship between disease activity and work productivity and between clinical evaluations and work productivity will be evaluated on the basis of the correlations with the TWPI for the baseline data.

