1. METHODOLOGY

The purpose of this statistical analysis plan is to provide detailed information on the statistical analysis of the data of study P13-990. The plan is based on the final protocol, incorporating administrative change 1, dated 17 December 2015.

1.1 *Introduction*

Ankylosing spondylitis (AS) and psoriatic arthritis (PsA) are both associated with often debilitating clinical symptoms, reduced functional impairment and significant impact on quality of life. As a consequence both diseases imply a significant economic burden, arising from both the direct costs of medical and disability. Health economics data becomes increasingly important to justify the costs of medicines.

Very limited data are available about the employment status and the work productivity of patients with AS and PsA in Belgium. The same is true for the impact of adalimumab treatment on employment status and work productivity.

The aim of this study is to analyse the employment status and work productivity of patients with AS and PsA before and after the start of adalimumab and to look at the relationship between employment status, work productivity, disease activity and clinical evaluations.

1.2 *Study Objectives and Endpoints*

1.2.1 *Study Objectives*

The main objective of the study is to observe in daily practice the evolution of work productivity over 18 months in AS and PsA patients after the start of adalimumab treatment.

The following questions were addressed:

- What is the employment status of AS and PsA patients with active disease before initiation of adalimumab?
- In the patients who work at baseline, what is their work productivity?
- Does adalimumab therapy enable people with AS and PsA to return to work or work more productively?

The secondary objectives are to:

- Investigate if there is a difference in evolution of employment status and work productivity after initiation of adalimumab treatment between AS and PsA patients throughout the study
- Investigate the relationship between disease activity and employment situation and the relationship between clinical evaluations and employment situation at baseline and after 18 months
- Investigate possible correlations between disease activity and work productivity and between clinical evaluations and work productivity

1.2.2 *Study Endpoints*

The primary endpoints is Total Work Productivity Impairment (TWPI) due to AS/PsA:

18 months versus baseline in all patients, measured by the WPAI-SHP questionnaire.

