(patient reported outcome)

The secondary endpoints are:

- Total Work Productivity Impairment (TWPI) due to AS and PsA separately: 18 months versus baseline in all patients, measured by WPAI-SHP questionnaire.
(patient reported outcome)
- Evolution over time of (observed for AS and PsA combined and separately) :
 - Number of patients that are employed at each assessed visit
 - Percentage of missed working hours (absenteeism) due to As/PsA 7 days prior to each visit
 - Assessment of the effect of As/PsA on the ability to do regular daily activities during the 7 days prior to each visit (activity impairment)
 - Assessment of the effect of As/PsA on productivity while working during the 7 days prior to each visit (presenteeism)
- Health Related Quality of Life (Patient reported outcome)
 - HAQ-DI (PsA)
 - DLQI (PsA)
 - HAQ-S (AS)
- Disease activity measures and clinical evaluations:
 - DAS28 (PsA)
 - BSA (PsA)
 - BASDAI (AS)
 - Acute phase reactants (CRP / ESR)
 - Physician assessment of disease activity by means of a visual analogue scale (VAS)
 - Patient assessment of disease activity (VAS)
 - Patient assessment of pain (VAS)

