5.10 Relation Between Work Status and Clinical Evaluations

For DAS28 score, BSA, DLQI score, HAQ-DI score, BASDAI total score, HAQ-S (total score and scores for pain during the past week, general health, and stiffness), physician and patient assessments of disease activity, and patient assessment of pain:

- For baseline, Month 18, and the last attended visit:
 - Descriptive statistics broken down by work status (Q1 of the WPAI).
 - Evaluation of the effect of work status (and indication) by means of analysis of variance.
- For the change between baseline and Month 18, and between baseline and the last attended visit, descriptive statistics broken down by work status (Q1 of the WPAI) at baseline.

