5.11 Relation Between Work Productivity and Clinical Evaluations

For baseline, the change between baseline and Month 18, and the change between baseline and the last attended visit, Spearman rank correlation between:

- Absenteeism, presenteeism, TWPI, percentage activity impairment and
- DAS28 score, BSA, DLQI score, HAQ-DI score, BASDAI total score, HAQ-S scores (total score and scores for pain during the past week, general health, and stiffness), physician and patient assessments of disease activity, patient assessment of pain.

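### SAP 5.10 and 5.11 leave ESR and CRP, a named disease-activity endpoint, out of the analyses relating disease activity to work outcomes, and SAP 1.10 does not declare it

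*SAP*

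**What the plan says.** SAP 1.2.1 repeats the protocol's secondary objectives. One is to "Investigate the relationship between disease activity and employment situation and the relationship between clinical evaluations and employment situation at baseline and after 18 months". Another is to "Investigate possible correlations between disease activity and work productivity and between clinical evaluations and work productivity".

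Protocol 10.2.2 sets out which measures belong to this group under "Disease activity measures and clinical evaluations recorded at each visit". The items are BASDAI, DAS28, BSA, acute phase reactants (CRP / ESR), the physician and patient VAS for disease activity, and the patient VAS for pain. Protocol 5.4 and SAP 1.2.2 list the same seven.

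Protocol 10.3.2 compares employed with non-employed patients on these measures at baseline and in the 18-month window. It says of the productivity relation that it "will be evaluated on the basis of the correlations with the TWPI for the baseline data". SAP 1.7 assigns Spearman correlation to the relation with TWPI at baseline and analysis of variance to the relation with work status. Neither section excludes a measure.

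The detailed sections work from fixed lists. SAP 5.10 runs from DAS28 to "physician and patient assessments of disease activity, and patient assessment of pain", and SAP 5.11 repeats the list, ending with "physician and patient assessments of disease activity, patient assessment of pain". ESR and CRP appear in neither. Their only planned analysis is the descriptive summary in SAP 5.9. SAP 1.10, which records changes from the protocol analysis, does not mention the omission.

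**The concern.** A programmer following SAP 5.10 and 5.11 as written would leave a named endpoint out of both objectives, and a reader of SAP 1.10 would not know that anything had changed. An oversight looks more likely than a decision. The same lists were widened beyond the disease-activity group to take in DLQI, HAQ-DI, HAQ-S and three extra HAQ-S items, and SAP 1.10 declares smaller changes than this one.

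The gap affects interpretation. TWPI is patient-reported. When it is correlated with activity, pain and function scores that the same patient supplies, part of any association may reflect a shared rating tendency. ESR and CRP are the only stand-alone laboratory measures among the endpoints. An association with them, or the lack of one, would be informative in a way that another self-rated scale is not.

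**Working it through.** **The plan's own figures.** Both documents take 200 patients, 65% working and 80% of those with 18-month data: 200 × 0.65 = 130 working at baseline, and 130 × 0.80 = 104, rounded to about 100. With n = 100, the 95% half-width is t(0.975; 99) × SD / √100. This gives 1.984 × 2.38 = 4.72 for SD 23.8 and 1.984 × 3.00 = 5.95 for SD 30.0, which reproduces the printed intervals (for example −10.0 ± 4.72 gives −14.7 to −5.3). The omission does not touch this table.

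**Endpoint list against analysis lists.**

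| Item in the group (SAP 1.2.2) | In SAP 5.10 | In SAP 5.11 |
|---|---|---|
| DAS28 (PsA) | yes | yes |
| BSA (PsA) | yes | yes |
| BASDAI (AS) | yes | yes |
| Acute phase reactants (CRP / ESR) | **no** | **no** |
| Physician VAS, disease activity | yes | yes |
| Patient VAS, disease activity | yes | yes |
| Patient VAS, pain | yes | yes |

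Six of the seven items are carried forward. With DLQI, HAQ-DI, the HAQ-S total and the three HAQ-S items, each list has 6 + 6 = 12 variables.

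**What is left, by indication.**

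- AS (8 variables): BASDAI, HAQ-S total, HAQ-S pain, general health and stiffness, patient activity VAS, patient pain VAS and physician VAS. Seven come from the patient and one from the physician. None is a laboratory value; Protocol 6.5.3 describes BASDAI as self-reported.
- PsA (7 variables): DAS28, BSA, DLQI, HAQ-DI and the three VAS ratings. By Protocol 6.5.3 and Appendix B, DAS28 contains an acute phase reactant, combined with joint counts and the patient's global rating. BSA is a graded extent of skin involvement (SAP 1.5).

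**How much of this the protocol promised.** Counting ESR and CRP as two variables, for all patients:

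- Productivity: TWPI at baseline only, so 2 × 1 = 2 correlations.
- Work status: baseline and Month 18, so 2 × 2 = 4 comparisons.

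The change correlations, the last-attended-visit analyses, the other three WPAI scores and the change summaries by work status are SAP additions.

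**Effect of adding both markers (12 to 14 variables).**

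- SAP 5.11: 4 WPAI scores × 12 × 3 analyses = 144 coefficients; 4 × 14 × 3 = 168. Increase 24.
- SAP 5.10: 12 × 3 time points = 36 analyses of variance; 14 × 3 = 42. Increase 6.

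The SAP states neither a significance level nor multiplicity control. If each coefficient were read at 5% and no association existed, the expected number of nominally significant ones would go from 144 × 0.05 = 7.2 to 168 × 0.05 = 8.4.

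**Would the added correlations be informative?** The detectable rho at 80% power, two-sided 5%, is tanh[(1.960 + 0.842) × √(1.06 / (n − 3))], using the Fisher transformation with the usual 1.06 variance factor for Spearman.

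| Setting | n | Detectable rho |
|---|---|---|
| All working patients, baseline | 130 | 0.25 |
| All, change to Month 18 | 104 | 0.28 |
| One indication, baseline, 70% share | 91 | 0.30 |
| One indication, baseline, 50% share | 65 | 0.35 |
| One indication, baseline, 30% share | 39 | 0.45 |

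The documents do not give the AS/PsA split, so the shares are assumptions. Missing laboratory values would lower n and raise these figures.

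**The case against.** The strongest reply is that the consequence is small. Protocol 10.3.2 calls the study essentially descriptive, the objective speaks only of possible correlations, TWPI itself is unaffected, and ESR and CRP are still summarised by visit and as change in SAP 5.9. SAP 1.7 is worded generally enough to cover acute phase reactants at baseline, so the gap could be called a mismatch between general and detailed text. All of this stands and limits the weight of the point. It does not remove it: the tables will be built from 5.10 and 5.11, and those lists leave the markers out.

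Three stronger readings are tempting, and the documents do not support them.

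- A reader might infer that both objectives rest only on subjective or composite scores. BSA is kept and is neither a questionnaire item nor a composite, so this fails for PsA.
- A reader might infer that ESR and CRP are the only safeguard against shared self-rating. The physician VAS comes from a different rater and is kept for both indications; in PsA, BSA and DAS28 add further information. The documents also give no figure for how strong a shared-rating effect would be.
- A reader might infer that everything missing from 5.10 and 5.11 breaches the protocol. Most of those analyses were introduced by the SAP.

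The objection is also right that adding the markers has a cost. The values are entered as recent ESR and CRP (SAP 1.5) and collected if available (Protocol 6.5.2). They need not fall in the seven-day WPAI recall period, and n may be smaller.

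**Conclusion.** The point holds in a limited form. One endpoint out of seven in the disease-activity group is absent from both sets of relation analyses, without declaration or reason. Measured against the protocol, the shortfall is 2 baseline TWPI correlations and 4 work-status comparisons, counting ESR and CRP separately. In AS the result is that no laboratory marker is related to any work outcome. In PsA the loss is partial, because DAS28 carries an acute phase reactant and BSA remains.

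This should be corrected, but it is a secondary matter and does not bear on the primary estimate or its precision. The conclusion rests on reading the lists in 5.10 and 5.11 as complete, which their wording supports, and on acute phase reactants belonging to the group that the objectives refer to, which three endpoint lists state.

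**What to change.** - **SAP 5.11:** add ESR and CRP to the variable list for the same analyses as the other measures (baseline, change to Month 18, change to last attended visit). Spearman correlation needs no change of method.
- **SAP 5.10:** add ESR and CRP at baseline, Month 18 and last attended visit, and to the change summaries. Run the analysis of variance on log values or ranks, on the expectation that these markers are skewed; the documents do not describe their distribution.
- **Both sections:** report n for each analysis, and note that the laboratory values are recent ones recorded where available.
- **If the exclusion is deliberate:** declare it with the reason in SAP 1.10. That would make the plan consistent, but would leave AS without a laboratory marker in these analyses.

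No new data are needed, since the values are already collected and summarised under SAP 5.9. The cost is a phrase in each of two sections, a sentence on transformation, 24 more Spearman coefficients and 6 more analyses of variance for all patients. If the correlations are also run within AS and PsA, the extra coefficients become 24 × 3 = 72. As none of these is adjusted for multiplicity, they should be presented as exploratory.

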6. SAFETY DATA

6.1 Serious Adverse Events

- By-patient list of individual data for SAEs that are not study-emergent.
- By-patient list of individual data for study-emergent SAEs.
- Frequency distributions of patients with study-emergent SAEs¹, and with study-emergent SAEs causing treatment discontinuation.
- Frequency distributions of patients with study-emergent SAEs by MedDRA SOC.
- Frequency distributions of patients with study-emergent SAEs by MedDRA SOC and PT¹.
- Frequency distributions of patients with study-emergent SAEs by MedDRA SOC, PT, and maximal severity.
- Frequency distributions of patients with study-emergent SAEs by MedDRA SOC, PT, and strongest relationship.

6.2 Non-Serious Adverse Events

- By-patient list of individual data for non-serious AEs that are not study-emergent.
- By-patient list of individual data for non-serious study-emergent AEs.
- Frequency distributions of patients with non-serious study-emergent AEs, and with non-serious study-emergent AEs causing treatment discontinuation.
- Frequency distributions of patients with non-serious study-emergent AEs in PTs for which the frequency of non-serious study-emergent AEs exceeds 1%¹.
This table will be titled ‘Patients with study-emergent non-serious adverse events above the frequency threshold (1%)’.
- Frequency distributions of patients with study-emergent SAEs by MedDRA SOC.
- Frequency distributions of patients with study-emergent SAEs by MedDRA SOC and PT¹.

¹ Information will also be reported in dedicated data files in order to report to ClinicalTrials.gov.
